## 7.7 Analysis of Pharmacodynamics

Not applicable.

## 7.8 Subgroups of Interest

### 7.8.1

A high-contrast, black and white image showing a series of horizontal bars of varying lengths and positions. The bars are set against a white background and appear to be composed of multiple thin lines. The bars are arranged in a staggered, non-overlapping pattern across the frame.

7.8.2

## 7.9 Other Analyses

No additional analyses are planned.

## **7.10 Interim Analysis (and Early Discontinuation of the Clinical Study)**

Two interim analyses for futility based on the primary efficacy endpoint will be conducted. The timing of these analyses will be at approximately 35% and 55% of all subjects with Week 8/EOT data. The plan for the interim analysis may be modified based on speed of recruitment. These analyses will be conducted by an Astellas statistician, with results reviewed by an Astellas IDMC. The Astellas statistician and other members of the Astellas IDMC are external to the study team. No one within the study team will be unblinded to the treatment allocation or interim results. Details of the interim analysis procedure, steps to maintain treatment blind in the study team and criteria for stopping the study will be described in an IAP.

## **7.11 Handling of Missing Data, Outliers, Visit Windows, and Other Information**

### **7.11.1 Missing Data**

As a general principle, no imputation of missing data for other variables will be done. Exceptions are the onset date of AE, start and stop dates of non-medication therapy, start and stop dates of previous and concomitant medication, onset date of FM symptoms, date of FM diagnosis and first/last dose date of double-blind study drug. In the listings of AEs, non-medication therapy, previous and concomitant medication and onset date of FM symptoms, diagnosis of FM, the first dose/last dose date of double-blind study drug will present the actual partial dates; imputed dates will not be shown.

For one of the sensitivity analyses for the primary efficacy endpoint and one of the sensitivity analysis for the FIQR secondary endpoint, multiple imputation will be used to impute missing data, using a discontinuation reason-based approach as described in Section 7.4.1.2. For analyses of selected efficacy endpoints, mBOCF, BOCF and/or LOCF will be used to impute the missing data. More details are described in Section 6.1 and Section 7.4.

### **Imputation of Adverse Event Onset Date**

For AEs, a missing or incomplete onset date will be imputed according to the following conventions:

If an onset date is missing or only the year is known, the imputed onset date will be the latest of the following non-missing dates:

- First dose date of double-blind study drug
- Randomization date + 1 day

If only the month and year is known for onset date, set the surrogate onset date to the first day of that month and then apply the following rules:

1. If the month and year of the onset date is prior to the month and year of the first dose of double-blind study drug, then the surrogate onset date will be the imputed onset date.

2. If the month and year of the onset date is on or after the month and year of the first dose of double-blind study drug, then the imputed onset date will be the latest of the following non-missing dates:
  - First dose date of double-blind study drug
  - Randomization date + 1 day
  - Surrogate onset date

If the imputed onset date is after a complete adverse event end date, the imputed onset date will be the same as the complete adverse event end date.

### **Imputation of Adverse Event End Date**

If only the day is missing for end date, set the surrogate end date to the last day of the month.

If the day and the month are missing for end date, set the surrogate end date month to December and set the day to the last day of the month (31).

If the year or the entire end date is missing, end date will not be imputed.

If an AE end date has been imputed, then apply the following rule:

1. If this imputed date falls after the end of participation in the study, then the surrogate end date will be set to the date of end of participation.

If the AE is ongoing (outcome is “NOT RECOVERED/NOT RESOLVED” or “RECOVERING/RESOLVING”) then the end date will remain missing.

### **Imputation of Start and Stop Dates of Non-Medication Therapy and Previous and Concomitant Medication Dates**

For Non-Medication Therapy and Previous and Concomitant Medications, a missing or incomplete start and stop dates will be imputed according to the following conventions:

If start date is missing or partial:

- if month is missing, use January
- if day is missing, use the first day of the month under consideration
- if year is missing, use year of the informed consent date
- if entire date is missing, use informed consent date

If stop date is missing or partial and medication or therapy is not ongoing:

- if month is missing, use December
- if day is missing, use the last day of the month under consideration
- if year or the entire date is missing, set to December 31st, 2099

If the imputed start date is after the stop date, then the imputed start date will be one day prior to the stop date.

If the medication or therapy is ongoing, the stop date will remain missing.

### **Missing Onset Date of FM Symptoms and Date of FM Diagnosis**

An incomplete onset date of FM Symptoms or date of FM diagnosis will be imputed according to the following conventions:

- Missing day, but month and year are present: the day will be imputed as the 15th day of the month.
- Missing day and month, but year is present: the day and month will be imputed as 30 June of the year.
- Missing year, but day and month are present: No imputations will occur, and the subject will be excluded from all summaries related to time since FM symptoms and diagnosis.
- Missing day, month and year: No imputations will occur, and the subject will be excluded from all summaries related to time since FM symptoms and diagnosis.
- If any such imputed date falls after the informed consent date, then the onset date will be taken as equal to the informed consent date.

### **Imputation of Study Drug Start Date Double-Blind Treatment Period**

For subjects who are randomized to double-blind study drug, the first dose date of double-blind study drug will be imputed if both of the following criteria are met:

- There is a missing or partial date for the first dose of double-blind study drug AND
- The number of tablets dispensed does not equal the number of tablets returned (including missing values).

If the first dose date of double-blind study drug is missing or partial, the first dose date of double-blind study drug is defined as the non-missing dispense date at randomization.

### **Imputation of Study Drug End Date Double-Blind Treatment Period**

For subjects who are randomized to double-blind study drug, the last dose date of double-blind study drug will be imputed if both of the following criteria are met:

- There is a missing or partial date for the last dose of double-blind study drug AND
- The number of tablets dispensed does not equal the number of tablets returned (including missing values).

If only the day is missing for the last dose date of double-blind study drug, the last day of the month under consideration will be used.

If the month and/or year are missing for the last dose date of double-blind study drug, then the latest of the following non-missing dates will be used:

11. last dispense date + 1 day OR
12. the date of the last vital sign measurement during the double-blind treatment period OR
13. 3.the date of the first dose of double-blind study drug in the double-blind treatment period + 1 day

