### **7.8    Handling of Missing Data, Outliers, Visit Windows, and Other Information**

As a general principle, no imputation of missing data will be done. Exceptions are the start and stop dates of AEs and concomitant medication and last dose date of double blind study drug. The imputed dates will be used to allocate the concomitant medication and AEs to a treatment group, in addition to determining whether an AE is/is not treatment emergent. The

imputed date of study drug will be used to calculate duration of study drug exposure. Listings of the AEs and concomitant medications and study dosing will present the actual partial dates; imputed dates will not be shown.

For one of the sensitive analyses for the primary efficacy endpoint, multiple imputation will be used to impute missing data, using 'Jump to Reference' algorithm for subjects who discontinue due to lack of efficacy or AEs and standard regression-based multiple imputation for subjects with missing data for other reasons. For analyses of selected efficacy endpoints, mBOCF, BOCF and/or LOCF will be used to impute the missing data. More details are described in [Section 7.4 Analysis of Efficacy]

See the SAP for details of the definition for windows to be used for analyses by visit.

Centers that do not enroll a sufficient number of subjects will be pooled for statistical analyses which includes study center according to a pre-specified algorithm in the SAP. The pooling decisions will be made and documented prior to study hard-lock.

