## 6.4 Other Variables

### 6.4.1 Exposure

For each subject, duration of exposure (defined as length of time on 8 weeks of treatment period) will be calculated in days, using the following formula:

- Duration of exposure = Date of last dose of study drug – Date of first dose of study drug +1,

where the date of first dose of study drug and the date of last dose of study drug are defined as the first study drug dosing date and the last study drug dosing date, as captured in the eCRF. Imputed dates for the first or last dose of study drug may be used to calculate exposure (Section 7.11.1).

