### 6.4.2 Percent Overall Compliance

Subjects will be instructed to take 2 tablets once per day, one tablet of 25 mg and 1 tablet of 5 mg.

Percent tablet-count compliance is defined as the number of tablets taken divided by the total number of tablets that should have been taken:

$$\frac{\text{Total number of tablets actually received during 8 weeks of treatment period}}{\text{Total number of tablets planned to receive during 8 weeks of treatment period}} \times 100$$

Where,

- Total number of tablets actually received during 8 weeks of treatment period = total number of tablets dispensed during 8 weeks of treatment period – total number of tablets returned during 8 weeks of treatment period.
- Total number of tablets planned to receive during 8 weeks of treatment period = 2 x duration of exposure. Duration of exposure will be calculated as described in Section 6.4.1

Double-blind study drug compliance for the entire double-blind treatment period will be calculated for subjects whose total number of tablets taken and the complete date of the first dose and the last dose of double-blind study drug are known.

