#### **7.11.4.2 Post Dosing Efficacy Observations**

For efficacy variables, observations will not contribute to the efficacy analyses during the treatment period if the subject’s last dose of double-blind study drug is as follows:

Any diary days or non-diary days which are > 4 days after the last dose of double-blind study drug will not be included in the analysis related to on-treatment time points and the EOT time point. This should be applied before implementing the visit windows in Section 7.11.4.3

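### A last-dose date with a missing day is imputed to month end with no cap, so up to 30 off-drug days can count as exposure and on-treatment time

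*SAP*

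**What the plan says.** SAP 7.11.1 imputes the last-dose date when it is missing or partial and the tablets dispensed and returned do not match (missing counts included). There are two branches:

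- Day missing, month and year known: "the last day of the month under consideration will be used". No upper bound follows.
- Month and/or year missing: the latest of three dates tied to recorded events, namely last dispensing plus one day, last vital signs in the treatment period, and first dose plus one day.

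Other imputed dates in SAP 7.11.1 are bounded. For adverse event end dates: "If this imputed date falls after the end of participation in the study, then the surrogate end date will be set to" the date participation ended. Imputed fibromyalgia onset and diagnosis dates may not pass the consent date.

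The last-dose date is then used in several places:

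- Exposure, SAP 6.4.1: "Imputed dates for the first or last dose of study drug may be used to calculate exposure". Protocol 7.8 is firmer: the "imputed date of study drug will be used to calculate duration of study drug exposure".
- Follow-up Day, SAP 7.1: counted from the last dose, with the date taken from 6.4.1. The treatment period runs to Follow-up Day 4.
- Efficacy exclusion, SAP 7.11.4.2: days more than "4 days after the last dose of double-blind study drug will not be included in the analysis related to on-treatment time points", nor for EOT. SAP 7.11.5.2 does the same for safety data.
- Adverse events, SAP 6.2.1: treatment-period events run to 4 days after the last dose, follow-up events from day 5.
- Compliance, SAP 6.4.2: planned tablets are "2 x duration of exposure", but the percentage is calculated only for subjects whose tablet count and complete first- and last-dose dates are known. SAP 7.3.2 repeats that restriction.

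**The concern.** The SAP recognises that an imputed date can run past what is possible for a subject and guards against it for two other kinds of date, but not for the last dose. As written, the imputed last dose can come after the visit at which the subject handed back the tablets, or after the subject has left the study. The better-documented subject can even receive the worse date: one with a known month is pushed to month end, while one with no month is anchored to a recorded event.

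At stake is the separation of on-drug from off-drug data. Exposure is overstated, follow-up safety data can be reported as on-treatment, and some early discontinuers can contribute off-drug pain scores to on-treatment weeks, against the SAP's own 4-day rule.

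**Working it through.** The plan states no figure on this point, so there is none to reproduce. The check is calendar arithmetic.

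**Inputs.** Month-end rule (SAP 7.11.1); treatment period ends at last dose + 4 days (SAP 7.1, 7.11.4.2); Week 8 pain window is Study Days 51 to 57 (SAP 7.11.4.3); follow-up visit is 14 days after the last dose, window ±2 days, with the diary returned there (protocol Table 1 and footnote a; 2.2.1). Let L be the true last-dose day and k the number of days by which imputation is late.

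**1. Size of the error.** The largest k arises when the last dose is on the 1st of a 31-day month: 31 − 1 = 30. Assume last-dose dates are spread evenly over a 365-day year. The sum of k is then 7 × 465 + 4 × 435 + 378 = 5,373, so the mean is 5,373/365 = 14.7 days. The error is at least 7 days for (7 × 24 + 4 × 23 + 21)/365 = 281/365 = 77% of positions.

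**2. Off-drug diary days available.** The diary runs to L + 14, at the latest L + 16. Days up to L + 4 are allowed anyway. The excess is 14 − 4 = 10 days, at most 16 − 4 = 12. The number actually admitted is the smaller of k and that excess.

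**3. Who reaches Week 8.** The last diary day must be at or after Day 51: L + 16 ≥ 51, so L ≥ 35. The first excess day must be at or before Day 57: L + 5 ≤ 57, so L ≤ 52.

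**4. Early discontinuer.** L = 43, diary kept to Day 57. With the true date the cutoff is Day 47 and Week 8 is missing. With k ≥ 10 the cutoff is Day 57 or later, so the whole Week 8 mean comes from true Follow-up Days 8 to 14, which is the SAP's own Week 10 window. At the half-life of about 65 hours in protocol 1.2, that is 192/65 = 3.0 to 336/65 = 5.2 half-lives after the last dose. Week 8 then counts as observed, so neither the multiple-imputation nor the mBOCF sensitivity analysis imputes it. Under the even-spread assumption, k ≥ 10 holds for (7 × 21 + 4 × 20 + 18)/365 = 245/365 = 67% of positions.

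**5. Completer.** L = 56, on the 1st of a 31-day month. Imputed last dose is Day 86; exposure is 86 days instead of 56, in the top category (65 days or more) of SAP 7.3.1. The treatment period ends on Day 90 instead of Day 60. The follow-up visit on Day 70 becomes Follow-up Day 70 − 86 = −16, that is, on-treatment. Its ECG becomes the EOT reading (SAP Table 31) and the Week 10 cell is left empty. The Week 8 pain score does not change, because its window closes at Day 57, already inside L + 4.

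**6. Per protocol set.** With a missing day the complete last-dose date is not known, so SAP 6.4.2 and 7.3.2 give no compliance value. SAP Table 2, criterion 5, sends missing compliance to case-by-case review. The 70% limit is not applied.

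**The case against.** The strongest reply is that the efficacy effect is inferred. SAP 7.11.4.2 does not mention imputed dates, and the one use protocol 7.8 names for the imputed study-drug date is duration of exposure. This stands as an ambiguity. It does not remove the point: SAP 7.1 takes the last-dose date for Follow-up Day from 6.4.1, where imputed dates are allowed, and the treatment period is defined by Follow-up Day.

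A second reply is rarity. The rule needs a known month and year, a missing day and mismatched tablet counts. Time of the last dose is captured at the pharmacokinetic visits (protocol 5.1.1), and discontinuers are asked to attend the EOT visit (protocol 6.1). This stands too.

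Three stronger readings are tempting but not supported:

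- A reader might infer that a subject who took every tablet could be scored below 70% and dropped from the per protocol set. If imputed dates entered the denominator, compliance would be d/(d + k) for d true days: 56/80 = 70.0% at k = 24, 56/81 = 69.1% at k = 25. The SAP never calculates these figures (step 6). What remains is a wording tension, since 6.4.2 borrows a duration that may be imputed before it excludes incomplete dates.
- A reader might infer that many weeks of off-drug scores could enter. A subject stopping on Day 28 could be imputed to Day 58, which seems to admit Days 33 to 57. On schedule, however, the diary is returned at about Days 42 to 44.
- A reader might infer that subjects lost to follow-up are hit most. The documents do not show this: a subject with no recorded month or year takes the other branch.

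**Conclusion.** The point holds and is minor. The month-end rule has no cap, and for an affected subject it can place the last dose up to 30 days late. Exposure and the treatment/follow-up split of safety data can shift by that amount. The effect on pain scores is limited to early discontinuers who keep the diary: about 10 to 12 off-drug days, reaching Week 8 only for those who stop at about Days 35 to 52. A completer's Week 8 score and the per protocol compliance limit are essentially untouched.

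This rests on two assumptions: the imputed date feeds Follow-up Day, as the cross-reference to SAP 6.4.1 implies, and follow-up visits keep to schedule. The number of partial dates is unknown; it may be few or none.

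**What to change.** Add one sentence to SAP 7.11.1: when only the day is missing, the imputed last-dose date is the earliest of the month end, the EOT or early-discontinuation visit, the final study drug return and the end of participation, but not before the first day of the recorded month or the first dose date. It must say final return, because drug is returned at Weeks 2, 4 and 8 and an earlier return would cut off genuine on-treatment data.

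For a completer with a last dose on Day 56 and an EOT visit no later than Day 59 (57 + 2), the largest error falls from 30 days to 59 − 56 = 3. For an early discontinuer, the remaining error depends on the gap between last dose and visit, which the documents do not give.

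The cost is that sentence and a small programming change, in the same form as the existing adverse event cap. The downside is small: a subject who took a dose after the capping date would have exposure slightly understated. It would also help to state in SAP 7.11.4.2 and 7.11.5.2 whether the imputed date applies there, and in 6.4.2 that compliance is never calculated from it.

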### **7.11.2 Outliers**

All values will be included in the analyses.

### **7.11.3 Values Below Limit of Quantification (BLOQ)**

For quantitative laboratory variables, values recorded as “<X” or “<=X” or “>Y” or “>=Y” will be imputed by “X” and “Y” respectively for descriptive statistics. This will be documented in a footnote to all summary tables and all output where such a replacement was performed.

ASP8062 plasma concentrations that are below the limit of quantification (BLOQ) will be set to 0 for calculating descriptive statistics.

### **7.11.4 Visit Windows for Efficacy Variables**

#### **7.11.4.1 Duplicate Values**

For daily average pain scores assessed by NRS [REDACTED] any data captured in the e-diary up to 2am in the morning of the following day will be assigned to the previous day in the derivation of Study Day (Section 7.1).

For all efficacy variables (either recorded in the e-diary or the tablet device), if more than one value is measured/recorded on the same Study Day, then the first of the values will be used. This should be applied before implementing the visit windows as described in Section 7.11.4.3

#### **7.11.4.2 Post Dosing Efficacy Observations**

For efficacy variables, observations will not contribute to the efficacy analyses during the treatment period if the subject’s last dose of double-blind study drug is as follows:

Any diary days or non-diary days which are > 4 days after the last dose of double-blind study drug will not be included in the analysis related to on-treatment time points and the EOT time point. This should be applied before implementing the visit windows in Section 7.11.4.3

#### **7.11.4.3 Visit Windows**

Subjects do not always adhere strictly to the visit timing in the protocol. Therefore, the designation of time points will be based on Study Day and Follow-Up Day (as defined in Section 7.1) rather than the nominal visit recorded in the eCRF.

To assign a measurement to a Week t during the double-blind treatment period, the first step consists of selecting all measurements falling within the double-blind treatment period as defined above. To further determine the Week t measurement, mutually exclusive relative day windows are used.

These day windows are defined to provide derived time points that correspond to the post baseline time points specified in the protocol.

Table 26 provides day windows for daily average pain scores assessed by NRS and rescue medication data. [REDACTED] Table 28

provides day windows [REDACTED]

Table 29 provides day windows for [REDACTED] HADS, [REDACTED] and [REDACTED]

**Table 26** [REDACTED]

Analysis Time Point	Visit Window (Day)
Baseline	Study days -6 to 1
Week 1	Study days 3 to 8
Week 2	Study days 9 to 15
Week 3	Study days 16 to 22
Week 4	Study days 23 to 29
Week 5	Study days 30 to 36
Week 6	Study days 37 to 43
Week 7	Study days 44 to 50
Week 8	Study days 51 to 57
EOT	Study day 3 to 57, where post-baseline data from the last 7 calendar days on or prior to the last FMSD scores will be used. If there is no post baseline data available EOT will be imputed using the baseline measurement.
Week 10	Follow up days 8 to 14

**Table 27 Day Windows: FMSD Questionnaire**

Analysis Time Point	Visit Window (Day)
Baseline	Study days -6 to 1
Week 1	Study days 3 to 8
Week 2	Study days 9 to 15
Week 3	Study days 16 to 22
Week 4	Study days 23 to 29
Week 5	Study days 30 to 36
Week 6	Study days 37 to 43
Week 7	Study days 44 to 50
Week 8	Study days 51 to 57
EOT	Study day 3 to 57, where post-baseline data from the last 7 calendar days on or prior to the last FMSD scores will be used. If there is no post baseline data available EOT will be imputed using the baseline measurement.
Week 10	Follow up days 8 to 14

**Table 28** [REDACTED]

Analysis Time Point	Visit Window (Day)
Baseline	Study days -6 to 1
Week 1	Study days 3 to 8
Week 2	Study days 9 to 15
Week 3	Study days 16 to 22
Week 4	Study days 23 to 29
Week 5	Study days 30 to 36
Week 6	Study days 37 to 43
Week 7	Study days 44 to 50
Week 8	Study days 51 to 57
EOT	Study day 3 to 57, where post-baseline data from the last 7 calendar days on or prior to the last FMSD scores will be used. If there is no post baseline data available EOT will be imputed using the baseline measurement.
Week 10	Follow up days 8 to 14

